The graded exercise test (GXT) on treadmill (h/p/cosmos pulsar 3p, Germany) was used to assess participant's endurance performance (i.e., VO2max and exhaustion time). Bruce protocol was adopted in the test (Bruce et al., 1973). The initial speed and grade of the GXT were set at 2.74 km/hr with grade of 10% and increases speed and grade every 3 min until

participants were voluntarily exhausted. Throughout endurance task, heart rate (HR) and perception of effort were measured every 2.5 min using an HR monitor (Polar H10, Finland) and Borg's 6-20 rating of perceived exertion (RPE)(Borg, 1982) to check whether participants meet the criteria of volitional exhaustion (Beltz et al., 2016). The time to exhaustion (TTE) and Maximum oxygen consumption (VO2max) were recorded as indicator of endurance performance.

Inhibitory control aspect of cognitive functions assessments

Followed by the manipulation conditions (i.e., 30-min Stroop task), inhibitory control was evaluated by a Flanker task (Eriksen & Eriksen, 1974; Friedman & Robbins, 2021). In the Flanker task, participants were presented with five arrows and instructed to respond as quickly and accurately as possible to the direction where the middle arrow is pointing (i.e., left or right). Types of trials are the congruent (i.e., >>>>) and incongruent (i.e., <<><<>.). The reaction time (RT) and accuracy (ACC) of incongruent trial were calculated as inhibitory control behaviors performance.

Furthermore, the neuroelectric activities during the Flanker task was measured by electroencephalographic (EEG). The EEG data was recorded from a 32-electrode Quik-Cap Neo Net (Compummedics Neuroscan Inc., Charlotte, NC, USA) based upon the Neuroscan system. Additionally, the EEGLAB (V8.3)7 and ERPLAB (V8.0)8 plugins based upon MATLAB (R2022a, Mathworks Inc.) were used to perform the offline data processing. Specifically, frontally (F3/Fz/F4) mean N2 amplitude and parietally (P3/Pz/P4) mean P3 amplitude for incongruent trial were extracted as neuroelectric marker of inhibitory control.

Manipulation check

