Specifically, all analyses followed intent-to-treat approach. The t-test (e.g., age, training experience) or chi-square test (e.g., gender, sports) were used separately to compare the difference in demographic characteristic between groups. For the manipulation check (e.g., subjective/objective mental fatigue), a four-way mixed-design ANOVA with 2 (GROUP: MT, WC) \times 2 (CONDITION: MF condition, CON condition) \times 3 (ASSESSMENT TIME: T1, T2, T3) \times 2 (Phase: baseline, post-intervention) was conducted to check the effect of manipulation on VAS-MF (i.e., subjective mental fatigue). A similar four-way mixed-design ANOVA with 2 (GROUP: MT, WC) × 2 (CONDITION: MF condition, CON condition) × 5 $(BLOCK: B1, B2, B3, B4, B5) \times 2$ (Phase: baseline, post-intervention) was conducted to check the effect of manipulation on accuracy of Stroop task (i.e., objective mental fatigue). For the primary outcomes (e.g., endurance performance, inhibitory control), the condition differences (i.e., delta value) in TTE, VO2max, and RT, ACC, N2 amplitude and P3 amplitude of Flanker task between MF condition and CON condition were calculated (CON - MF). Subsequently, the post-intervention of Δ TTE, Δ VO2, Δ RT, Δ ACC, Δ N2 and Δ P3 between groups were separately compared by one-way ANCOVA while controlling baseline of delta value. Furthermore, the one-way ANCOVA was also separately conducted to compare the post-intervention of AMQ scores and mental fatigue-related change of BRUMS-C scores between groups while controlling baseline of scores. All analyses were conducted using SPSS v.26 (SPSS Inc., Chicago, IL), with a significance level set at p < 0.05.

REFERENCE

- Beltz, N. M., Gibson, A. L., Janot, J. M., Kravitz, L., Mermier, C. M., & Dalleck, L. C. (2016). Graded exercise testing protocols for the determination of VO2max: Historical perspectives, progress, and future considerations. *Journal of Sports Medicine*, 2016, 3968393. https://doi.org/10.1155/2016/3968393
- Borg, G. A. (1982). Psychophysical bases of perceived exertion. *Medicine & Science in* Sports & Exercise, 14(5), 377–381. https://doi.org/10.1249/00005768-198205000-00012
- Brown, D. M. Y., Graham, J. D., Innes, K. I., Harris, S., Flemington, A., & Bray, S. R. (2020). Effects of prior cognitive exertion on physical performance: A systematic review and meta-analysis. *Sports Medicine*, 50(3), 497-529. https://doi.org/10.1007/s40279-019-01204-8

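### Six listed primary outcomes are each tested at 0.05 with no claim rule or adjustment; if any one may count as success, the false-positive rate is 26.5% for independent tests (about 24% to 14% at correlations of 0.3 to 0.8)

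*Combined protocol and SAP*

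**What the plan says.** The Statistical Analysis Plan describes "primary outcomes (e.g., endurance performance, inhibitory control), the condition differences (i.e., delta value) in TTE, VO2max, and RT, ACC, N2 amplitude and P3" amplitude, each taken as the control-condition value minus the mental-fatigue value. The six post-intervention differences "between groups were separately compared by one-way ANCOVA while controlling baseline of delta value". The section closes by covering all analyses "with a significance level set at p < 0.05".

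The six fall into two domains. Under Endurance performance assessment, TTE and VO2max "were recorded as indicator of endurance performance". Under Inhibitory control aspect of cognitive functions assessments, Flanker RT and accuracy are the behavioural measures, and N2 and P3 amplitude the neuroelectric ones.

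Other tests have a different standing. The plan opens the mental fatigue analyses with "For the manipulation check (e.g., subjective/objective mental fatigue), a four-way mixed-design ANOVA", and a similar ANOVA "was conducted to check the effect of manipulation on accuracy of Stroop task (i.e., objective mental fatigue"). A further set of ANCOVAs is used to "compare the post-intervention of AMQ scores and mental fatigue-related change of BRUMS-C scores between groups"; these are not listed among the primary outcomes.

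The Abstract's hypothesis predicts less subjective and objective mental fatigue in the mindfulness group, and smaller fatigue-related changes in both domains. It does not say which results would confirm this.

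**The concern.** The hypothesis is about constructs, and the tests are on individual measures. One construct has two measures and the other has four, and nothing links a pattern of significant results to a conclusion about a construct or about the trial. The plan therefore does not exclude reporting that mindfulness protects endurance, or that the trial succeeded, on the strength of one significant ANCOVA.

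If that happens, 0.05 is the error rate of a single test and not of the claim. A reader cannot tell from the document which kind of claim will be made, and so cannot tell what error rate the reported p-values carry.

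**Working it through.** **Inputs.** From the Statistical Analysis Plan: six primary ANCOVAs, each at 0.05. The F test for two groups rejects in either direction. From the Abstract: 26 and 27 participants, so each ANCOVA has 53 − 3 = 50 error degrees of freedom if all are analysed. The documents give no familywise error rate, power calculation or between-outcome correlations, so there is no planned figure to reproduce, and the correlations below are assumptions.

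**Independent tests, no true effect, either direction.**
- Any of six: 1 − 0.95^6 = 0.265.
- Any of two (endurance): 1 − 0.95^2 = 0.0975.
- Any of four (inhibitory control): 1 − 0.95^4 = 0.185.

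**Bounds under any dependence.** 6 × 0.05 = 0.30, 2 × 0.05 = 0.10 and 4 × 0.05 = 0.20. The independent-test values are ceilings only when the test statistics are jointly normal.

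**Equally correlated normal statistics.** P(at least one |Z| > 1.96), by numerical integration over the common factor:

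| Correlation | Any of six | Endurance (2) | Inhibitory control (4) |
|---|---|---|---|
| 0 | 26.5% | 9.8% | 18.5% |
| 0.3 | 24.1% | 9.5% | 17.4% |
| 0.5 | 20.7% | 9.1% | 15.6% |
| 0.7 | 16.4% | 8.3% | 13.0% |
| 0.8 | 13.9% | 7.8% | 11.4% |

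**Correlation within task only.** Treadmill measures may correlate with each other, and Flanker measures with each other, but not across tasks. This was simulated with the planned ANCOVA (26 and 27 participants, assumed baseline-to-post correlation 0.5, 40,000 trials). At within-task correlations of 0, 0.3, 0.5 and 0.8, any of six is significant in 26.6%, 25.4%, 23.6% and 18.1% of trials.

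**Requiring at least one measure in each domain.** By inclusion–exclusion this is endurance + inhibitory control − any of six.
- With no effect in either domain and independent tests: 0.0975 + 0.1855 − 0.2649 = 0.018.
- Under equal correlations of 0.3, 0.5, 0.7 and 0.8: 2.8%, 3.9%, 5.0% and 5.4%.
- If endurance truly is affected and inhibitory control is not, a false claim for both can reach the inhibitory-control rate, 18.5% for independent tests.

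**Results favouring mindfulness only** (nominal 2.5% per test).
- A favourable sign fixed for all six: 1 − 0.975^6 = 14.1% if independent, 12.2% at a correlation of 0.3 and 6.9% at 0.8.
- Either sign of N2 and P3 read as favourable, since the document fixes no sign for them: 1 − 0.975^4 × 0.95^2 = 18.4% if independent.

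**Effect of Holm.** In the within-task simulation, Holm over all six gives at least one rejection in 4.8%, 4.8%, 4.6% and 3.5% of null trials. Holm applied separately within each domain leaves 9.3%, 9.4%, 8.9% and 7.1% for a rejection in either domain.

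**The case against.** The strongest reply is that the plan never says any one of six is enough. Separate comparisons fit outcome-by-outcome claims just as well, and then each test keeps its own 5% error rate and no adjustment is needed. This stands as far as it goes: what is established is a missing claim rule, and 26.5% is the consequence of one reading that the plan leaves open. It does not remove the point, because the hypothesis is stated at the level of the domains and the document does not limit claims to single outcomes.

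A second reply is that the hypothesis is directional, so counting both directions overstates the risk of a false claim for mindfulness. With all signs fixed, the rate is about half. It is still roughly three to six times the nominal 2.5% (6.9% to 14.1%).

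Third, the outcomes are surely correlated. They may be, but even a common correlation of 0.8 across all six leaves 13.9%, nearly three times nominal, and that requires treadmill and Flanker measures to correlate as strongly across tasks as within them.

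Fourth, the primary outcomes are introduced as examples, so six is the number listed and not a closed set. That is correct, and an open list does not help the plan. Finally, the Design and Sample section cites a registration that is not available here and that may designate a primary outcome. The finding is therefore about this document.

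**Conclusion.** The concern holds. The document lists six primary outcomes, tests each at 0.05 and gives no ranking, success rule, alpha split or adjustment. If one significant result may carry the trial, the either-direction error rate is 26.5% for independent tests and about 24% to 14% at common correlations of 0.3 to 0.8. If one result may carry its own domain, the rate is about 8% to 10% for endurance and 11% to 19% for inhibitory control over the same span.

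These figures assume no true effect on the outcomes counted, jointly normal test statistics and the stated correlations, none of which comes from the documents. There is no inflation under an all-six rule or strictly per-outcome claims. The gap affects how results may be interpreted and does not invalidate the trial, so it should be fixed but is not fatal.

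**What to change.** Apply the Holm procedure across the six listed primary ANCOVAs at a familywise 0.05. Compare the smallest p-value with 0.05/6 = 0.0083, the next with 0.05/5 = 0.01, then 0.0125, 0.0167, 0.025 and 0.05, stopping at the first failure. Report unadjusted and adjusted p-values for all six, and call a primary outcome positive only if its adjusted p-value is below 0.05. A single family of six covers both trial-level and domain-level claims; separate families per domain would not.

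Report the AMQ and BRUMS-C ANCOVAs as supportive, and the VAS-MF and Stroop accuracy ANOVAs as the manipulation checks the plan calls them. All stay outside the family and support no primary claim.

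If an earlier dated plan or record specifies a ranking or adjustment, cite and follow it. Otherwise label the Holm adjustment post hoc: the document is dated 19 December 2023, and the Design and Sample section gives 10/1/2023 as the end of conduct, 343 days earlier if read as 10 January.

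**Cost.** No new data and no refitted models, because the adjusted p-values follow from the six unadjusted ones. A post hoc adjustment does not restore prespecification. With 26 and 27 participants, all analysed, and 50 error degrees of freedom (noncentral t), the price in power is:

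| Holm step | Level | Effect detectable with 80% power (residual SD) | Power for 0.785 SD |
|---|---|---|---|
| 1 | 0.0083 | 0.99 | 55% |
| 2 | 0.01 | 0.97 | 57% |
| 3 | 0.0125 | 0.95 | 61% |
| 4 | 0.0167 | 0.92 | 65% |
| 5 | 0.025 | 0.87 | 71% |
| 6 | 0.05 | 0.785 | 80% |

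Stating that each outcome is claimed only for itself would avoid this loss, but it would give up any trial-level or domain-level conclusion from a single significant measure.

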Effect of Mindfulness Training on Mental Fatigue-Related Impairments of Endurance Performance and Inhibitory Control in Athletes: An Event-Related Potential Study

Principal Investigator: [name]

NTC: NCT05452460 Date: December 19, 2023

ABSTRACT

Purpose: This study utilized a longitudinal design to examine the effect of mindfulness training on mental fatigue-related impairments of endurance performance and inhibitory control aspect of neurocognitive functions in athletes. Methods: In this randomized controlled trial (RCT) study, specifically, fifty-three aged between 18 to 25 years of college athletes were randomly assigned to either a mindfulness training group (MT, n = 26) or a waiting-list control group (WC, n = 27) after completing the pre-test. MT group engaged mindfulness program in a 60-min session per week for eight weeks, whereas WC were asked to maintain regular life and routine training. The change in dispositional mindfulness was evaluated by Athlete Mindfulness Questionnaire (AMQ) before and after the intervention. Participants completed the two 30-min manipulation conditions by Stroop task [i.e., mental fatigue condition (MF) or control condition (CON)] in both baseline and post-intervention, respectively. Before (T1) and after (T2) the 30 min manipulations, subjective mental fatigue and mood were measured using a visual analogue scale for mental fatigue (VAS-MF) and Brunel mood scale-Chinese (BRUMS-C), respectively. The participants then completed the Flanker task [i.e., reaction time (RT) and accuracy (ACC)] and its induced ERP components (i.e., N2 and P3) were recorded, and subjective mental fatigue was evaluated by VAS-MF immediately after the Flanker task (T3). Following, endurance performance [i.e., time to exhaustion (TTE] and VO2max] of participants were evaluated using graded exercise test (GXT). Additionally, VAS for motivation in task (VAS-M) was used to evaluate motivation for completing tasks after the Flanker task and GXT. Expected results: It was hypothesized that MT will exhibit less subjective and objective of mental fatigue, and exhibit less mental fatigue-related changes in endurance performance and inhibitory control-aspect of neurocognitive functions.

METHODS

Design and Sample

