This study examining mindfulness training on mental fatigue-related impairments of endurance performance and inhibitory control aspect of neurocognitive functions in athletes was registered at ClinicalTrials.gov (NCT05452460). The actual conduct of this study was from 17/2/2022 to 10/1/2023. Initially, one hundred and twenty-five potential participants were recruited via advertisements and personal contact form several sports team in Taiwan. After screening the eligibility and participation interested, the fifty-three were included in this study, and eligible participants who were (1) regular sports training at least 4 hours weekly, (2) normal or corrected-to-normal vision, (3) right-handedness, (4) no physical limitation or injury in lower limbs before and during the study, (5) no diagnosed or self-reported neurological disorders (e.g., epilepsy), (6) no diagnosed or self-reported major psychiatric illness (e.g., major depression, schizophrenia), and (6) no major previous experience with mindfulness training.

Procedure

In this study, participants visited the lab four time, they completed the two 30-min manipulation conditions by Stroop task [i.e., mental fatigue condition (MF) or control condition (CON)] in both baseline and post-intervention, respectively. Before (T1) and after (T2) the 30 min manipulations, subjective mental fatigue and mood were measured using a visual analogue scale for mental fatigue (VAS-MF) and Brunel mood scale-Chinese (BRUMS-C), respectively. The participants then completed the Flanker task [i.e., reaction time (RT) and accuracy (ACC)] and its induced ERP components (i.e., N2 and P3) were recorded, and subjective mental fatigue was evaluated by VAS-MF immediately after the Flanker task (T3). Following, endurance performance [i.e., time to exhaustion (TTE] and VO2max] of participants were evaluated using graded exercise test (GXT). Additionally, VAS for motivation in task (VAS-M) was used to evaluate motivation for completing tasks after the Flanker task and GXT.

Prior to each visit, participants received the following instructions: do not do training vigorously the day before test, do not consume a food or beverage containing caffeine and alcohol 12 h before test, and do not sleep less than 7 h before the visit.

Outcome measures

Endurance performance assessment

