Subjective mental fatigue assessment. Both in the baseline and post-intervention, the visual analog scale for mental fatigue (VAS-MF) was used to assess changes in perceived mental fatigue before (T1) and after (T2) two separate experimental conditions (i.e., 30-min of 100% incongruent Stroop task or 100% congruent version Stroop task), and after Flanker task (T3). The VAS has been used to extensively evaluate the change in perceived mental fatigue caused by prolonged cognitive task (Brown et al., 2020; Van Cutsem et al., 2017).

Objective mental fatigue assessment. Both in the baseline and post-intervention, participants completed either a 30-min 100% incongruent Stroop task or 30-min 100% congruent Stroop task. Accuracy in both Stroop tasks was calculated as an index of objective mental fatigue (Filipas et al., 2018; Smith et al., 2015).

Dispositional mindfulness assessment

The changes in dispositional mindfulness was assessed using the 16-items (5-Likert

scale) athlete mindfulness questionnaire (AMQ)(Zhang et al., 2017). Higher mean scores indicate a higher level of dispositional mindfulness. Changes in mindfulness total scores and subscale scores from baseline to post-intervention were examined.

Mood state assessment

The change in mood state before and after manipulation conditions was assessed using the Brunel mood scale- Chinese (BRUMS-C), which contains 23 items and divided into six respective sub-scales such as anger, confusion, depression, fatigue, tension, and vigor (Zhang et al., 2014).

Statistical Analysis Plan

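### The planned ANCOVA on Δ (CON - MF) has no term for condition order, which costs precision if order varied between participants; the documents do not say whether it did

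*Combined protocol and SAP*

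**What the plan says.** The Procedure section reports that "participants visited the lab four time, they completed the two 30-min manipulation conditions by Stroop task", and that both conditions were done at baseline and again after the intervention. Two conditions in two phases over four visits imply one condition per visit. That is an inference, but a natural one, because each session ends with a treadmill test to exhaustion. The Manipulation check section also treats the two conditions as separate.

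The Statistical Analysis Plan forms differences in TTE, VO2max and the Flanker RT, accuracy, N2 and P3 "between MF condition and CON condition were calculated (CON - MF". The six post-intervention differences then "were separately compared by one-way ANCOVA while controlling baseline of delta value". The two manipulation-check ANOVAs have group, condition and phase as factors, plus assessment time (VAS-MF) or block (Stroop accuracy).

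No model contains order, visit or sequence. No section states which condition came first, whether order was randomised or counterbalanced, how far apart the visits were, or whether there was a familiarisation session. The only randomisation described is to study arm: participants "were randomly assigned to either a mindfulness training group (MT, n = 26) or a waiting-list control group (WC, n = 27) after completing the pre-test".

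**The concern.** A Flanker task, a 30-minute Stroop task and an exhaustive treadmill test, repeated over four visits, are open to practice, pacing and familiarisation effects. When the two halves of a difference come from different visits, any first-to-second-visit change becomes part of that difference. Its sign depends on which condition came first.

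If order varied between participants, Δ therefore contains a known, measurable source of variation that the planned ANCOVA counts as error. Δ underlies all six primary comparisons in a trial of 53 people, so avoidable error variance matters. If order was the same for everyone, the issue is a different one: the visit change is then part of every participant's Δ and of the condition main effect in the manipulation checks.

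**Working it through.** The documents contain no sample-size calculation, SD or visit effect, so there is no figure to reproduce. What follows is an illustration over a range.

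**Inputs.** From the documents: 26 and 27 participants, and α = 0.05 (taken as two-sided). Assumed: baseline-to-post correlation of Δ of 0.3; order split about half and half; visit effect k = 0.25 or 0.5, in units of the SD of Δ among people with the same order; true group effect 0.77 SD, which has 80% power at this size with no visit effect and no covariate.

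**Step 1: how order enters Δ.** Let k be the second-visit minus first-visit change. Then Δ shifts by +k if MF came first and by -k if CON came first. With a half-and-half split, the variance of Δ is multiplied by 1 + k²: 1.06 at k = 0.25 and 1.25 at k = 0.5.

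**Step 2: residual variance in the planned ANCOVA.** With c the covariance of baseline and post-intervention Δ, it is (1 + k²) - c²/(1 + k²). Here c = 0.3 + k² if each person keeps the same order in both phases, 0.3 if order is redrawn, and 0.3 - k² if it is reversed. With order terms fitted it is 1 - 0.3² = 0.91. At k = 0.5:

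- same order: 1.25 - 0.55²/1.25 = 1.008
- redrawn: 1.25 - 0.30²/1.25 = 1.178
- reversed: 1.25 - 0.05²/1.25 = 1.248

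**Step 3: standard error of the group difference.** SE = √[residual variance × (1/26 + 1/27)], and 1/26 + 1/27 = 0.0755. This gives 0.276, 0.298 and 0.307, against 0.262 with order terms: about 5%, 14% and 17% larger. Simulation, which also counts the estimated coefficients, gives 0.278, 0.301 and 0.310 without order terms, against 0.266, 0.269 and 0.266 with them.

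**Step 4: power.** Simulated, 4,000 runs per setting, effect 0.77 SD:

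| Order across phases | k = 0.25, without / with order | k = 0.5, without / with order |
|---|---|---|
| Same in both | 80.4% / 80.7% | 77.4% / 81.0% |
| Redrawn | 78.5% / 79.4% | 70.7% / 79.2% |
| Reversed | 76.9% / 80.5% | 67.9% / 80.4% |

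Separate runs with an effect of 0.8 SD and k = 0.5 gave 79% / 83%, 75% / 83% and 71% / 83%; a repeat gave 80% / 83% for the same-order case. Taken together, and allowing for simulation error, the loss is about 0 to 4 points at k = 0.25 and about 3 to 12 at k = 0.5. Simulated type I error of the planned model in these cases was 4.2% to 5.4%.

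**Step 5: chance imbalance of order between arms.** Its SD in the group difference is 2k√(0.25/26 + 0.25/27) = 0.137 at k = 0.5. Combined with the order-adjusted SE for the redrawn case, √(0.269² + 0.137²) = 0.302, which matches the unadjusted 0.301. It is the same loss seen from another side, not an additional one.

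**Step 6: counterbalancing within arm at post-test (k = 0.5).** The true SE falls to about 0.271, but the planned model still reports about 0.301, so intervals are about 11% too wide (0.301/0.271 = 1.11). Power was 73.5%, against 83% with order terms.

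**Step 7: one order for everyone.** The group contrast was unbiased, with type I error of about 5% and power of about 82%. This assumes the same visit effect in both arms.

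**The case against.** The strongest reply is that the documents show only a reporting gap. Whether an order term helps, or can be fitted at all, depends on a fact they do not give. That stands, and it is why the recommendation is conditional. It does not reduce the point to one of wording: under any scheme with varying order, the stated model is less efficient than an equally simple alternative.

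The size is also open to challenge. The outcome is taken after two full baseline sessions, so familiarisation may have faded. Assuming 0.5 SD at baseline but 0.25 SD at post-test, power without and with order terms is 84% and 83% (same order), 81% and 82% (redrawn), and 79% and 84% (reversed). Nor need the six outcomes share one visit effect. Both objections stand.

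Three stronger readings are tempting but not supported:

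- **That order confounds the primary comparison.** This needs order to be associated with arm. An assumed 70% against 30% split at post-test would bias the contrast by about 0.40 SD at k = 0.5 and raise type I error to 27%, but nothing in the documents suggests such a link. Allocation followed the pre-test, so baseline order can differ between arms only by chance.
- **That chance imbalance is a further harm.** Step 5 shows it is already inside the standard error.
- **That the manipulation check is wholly confounded with visit.** This applies only to the CONDITION main effect, and only if order was fixed. The VAS-MF model includes a rating before the manipulation and the Stroop model includes block, so the CONDITION × TIME and CONDITION × BLOCK interactions remove a constant visit shift. Only a visit effect on change within the session would remain.

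**Conclusion.** The concern holds as a conditional loss of precision. If order varied independently of arm, the planned ANCOVA remains a valid test but carries avoidable error. The loss is small at a visit effect of 0.25 SD and moderate at 0.5 SD, and within-arm counterbalancing would leave the intervals too wide. These sizes rest on an assumed visit effect, equal in both phases unless stated otherwise, an assumed correlation of 0.3 and a half-and-half order split. They show a range and do not estimate what happened in this trial.

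If order was the same for everyone, the between-group comparison of Δ stands provided practice is equal in both arms. What is limited then is interpretation: the CONDITION main effect and the within-arm Δ cannot be separated from visit number. The documents do not show which scheme applies.

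**What to change.** 1. State the order scheme: which condition came first, how that was decided, and whether it was the same at baseline and after the intervention.
2. If order varied, add post-intervention ORDER (MF-first or CON-first) as a fixed factor to each of the six Δ ANCOVAs, and baseline ORDER as well if it differed between phases. Study conduct ended on 10/1/2023 and the document is dated December 19, 2023, so label the adjustment post hoc if it is added after the data were seen, and report it beside the planned analysis.
3. If order was the same for everyone, keep the planned ANCOVA and say that it relies on equal practice in both arms. Base the manipulation check on CONDITION × TIME and CONDITION × BLOCK, and do not attribute the CONDITION main effect or the within-arm Δ to mental fatigue alone.

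The planned ANCOVA has 53 - 3 = 50 residual degrees of freedom; one or two order terms leave 49 or 48. In the runs above, adding them cost essentially no power even at a visit effect of 0.25 SD. No new data are needed if visit order was recorded, which is assumed here and not stated in the documents.
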